4.1 SDS with reference to normal population

The height-for-age SDS with reference to the normal population will be calculated using the 'WHO Child Growth Standards'⁵⁻⁷ from birth to 5 years and the 'WHO Reference 2007 for boys and girls, 5-19 years'⁶ for children older than 5 years.

The tables of the WHO Child Growth Standards are accessible in electronic format at www.who.int/childgrowth/standards/en; and the tables of the WHO Reference 2007 can be found at www.who.int/growthref.

The following datasets available from the WHO websites will be used:

- lhfa_boys_p_exp.txt
- lhfa_girls_p_exp.txt
- hfa_boys_perc_WHO2007_exp.txt
- hfa_girls_perc_WHO2007_exp.txt

The WHO standard tables assume that $L=1$ for all ages.

All SDS for children below 24 months are length-based and height-based otherwise. This means for children aged below 24 months (<731 days) and measured standing, the height will be converted to recumbent length by adding 0.7 cm; and for children aged 24 months or above who are measured in recumbent position, the length will be converted to standing height by subtracting 0.7 cm.

4.2 SDS with reference to achondroplasia population

The height-for-age SDS with reference to the achondroplasia population will be calculated on tabulations of population means (M), standard deviations (MxS), and coefficient of variation (S) Merker at al. (2018)⁹. Descriptive statistics and fitted values of L, M, and S for age are summarized in Supporting Information Table 2⁹.

L, M, and S values for finer ages values (age in exact years) will be interpolated between the neighbouring table values. The Merker standard tables assume that L=1 for all ages.

The same method for the standing height and the recumbent length will be applied. No adjustment to convert standing height and recumbent length will be applied when calculating the SDS with reference to the achondroplasia population.

Appendix 2 shows the calculation of the SDS for 3 examples.

2.2.4. Achondroplasia-Related Symptoms, Test, and Treatment

Achondroplasia-related symptoms will be collected according to relevant body systems and severity (mild, moderate, and severe).

Achondroplasia-related tests and treatment are also collected in the eCRF.

After the initial report on an important medical symptom, test, or treatment, the investigator should follow-up on the severity status of the medical symptoms, determine whether the symptom is ongoing or is resolved, and assess the outcome of a potential treatment until the child's participation in the study has ended.

2.2.5. Non-achondroplasia-Related Conditions of Medical Significance

Information concerning the diagnosis of any non-achondroplasia-related conditions of medical significance, including start and stop dates, should be reported. Information may be provided by parent(s) / legal guardian(s) or by the child if this is applicable.

3. Overall Study Design and Plan

This is a registry study in children with achondroplasia, aged 0-10 years, to be conducted at multiple clinical centers in several countries. Childrens' information will be collected in the registry at baseline and at every 3-month interval visits, for a maximum of 5 years. There will be a Screening visit, a Baseline visit, 3-month interval visits, a yearly visit (± 3 weeks), and a Final visit.

The children may continue study participation until:

- Growth plates are considered to have fused, defined as standing height gain less than 1 cm within the last 6 months
- The child has reached the end of puberty (Tanner Stage V)

- The child is enrolled in an interventional study
- The child has participated in the study for 5 years
- The child is considered lost to follow-up

3.1. Overall Design

CCI

The study will enroll participants in the following approximate proportions:

- 40% 0-5y
- 40% 5-10y
- 20% 10-15y

3.3. Study Population

Children between 0 years and 15 years of age with achondroplasia documented by clinical diagnosis.

3.4. Treatments Administered

No investigational treatment will be administered.

3.5. Method of Assigning Subjects to Treatment Groups

No investigational treatment will be administered.

3.6. Blinding and Unblinding

Not applicable.

3.7. Schedule of Events

A detailed schedule of events for the study is provided in [Table 2](#).

Table 2: Schedule of Events

Procedure	Screening Visit ^a (Visit 0)	Baseline Visit (Visit 1) ^b	Every 3 Months ^c (±3 weeks)	Every year (±3 weeks)	Final Visit ^{c,d} (±3 weeks)
Informed consent and assent (as applicable)	X				
Eligibility criteria	X	X			
Demographics	X				
Medical and surgical history	X	X			
Physical examination		X	X		X
Waist circumference		X		X	X
Genetic confirmation of achondroplasia ^e		(X)			
Anthropometric measurements		X	X		X
Achondroplasia-related symptoms, tests, and interventions		X	X		X
Non-achondroplasia-related symptoms, tests, and treatments ^f		X	X		X
Tanner stage of puberty ^g		X	X		X
Collection of blood sample ^h		X		X	X

a. Within 1 month before Baseline visit.

b. Screening visit and Baseline visit can be combined, if applicable.

c. Visits are scheduled relative to the date of the Baseline visit.

d The Final visit is conducted after termination criteria are met or after a decision to withdraw the child from the study.

e. If not available in medical records, then the result of genetic testing should be available as soon as possible, but not later than at the Final Visit.

f. Any non-achondroplasia-related important medical conditions and any treatment based on the medical judgment of the investigator that may affect the child's growth trajectory.

g. Only for children ≥ 7 years of age (providing the investigator confirms there is no suspicion of a diagnosis of precocious puberty).

h. Fasting blood sample for biomarker analyses is required to be drawn in the morning. Sampling can be done, e.g., at a separate visit in the clinic, in the home by a visiting nurse, or at a local laboratory, whatever is most convenient and appropriate for the child's well-being.

4. Statistical Analysis and Reporting

4.1. Introduction

Data processing, tabulation of descriptive statistics, calculation of inferential statistics, and graphical representations will be performed primarily using SAS (release 9.4 or higher).

Continuous (quantitative) variable summaries will include the number of subjects (n) with non-missing values, number of missing values (if applicable), mean, standard deviation (SD), median, minimum, and maximum. Continuous variables may be classed into groups and analyzed as a categorical variable when appropriate.

Categorical (qualitative) variable summaries will include the number of subjects (n) with non-missing values, number of missing values, frequency, and percentage of subjects who are in the particular category or each possible value. In general, the denominator for the percentage calculation will be based upon the total number of subjects in the study population with non-missing data.

The minimum and maximum will be reported with the same degree of precision (i.e., the same number of decimal places) as the observed data. Measures of location (mean and median) will be reported to 1 degree of precision more than the observed data and measures of spread (SD) will be reported to 2 degrees of precision more than the observed data.

Percentages will be presented to 1 decimal place, unless otherwise specified.

4.2. Data Snapshot and Data Monitoring

Data snapshot will be performed on a regular basis. This SAP describes the analytical principles and statistical techniques to be employed for both data snapshots and final analysis.

The sponsor may also request additional analysis during the study to analyze a particular research question that emerges during the course of the study.

A data safety monitoring board will not be used in this study.

5. Analysis Populations

All analyses will be conducted on all enrolled children. The enroll set includes consented, screened, and eligibility-verified children.

Data after procedures or treatments that may affect height growth will be excluded from the analysis of anthropometric parameters. The Sponsor will review the subject-level data on an ongoing basis, providing information about procedures or treatment that may affect growth velocity.

6. General Issues for Statistical Analysis

6.1. Statistical Definitions and Algorithms

6.1.1. Baseline

The observation recorded at Baseline visit (Visit 1) will be used as the baseline observation for all calculations of change from baseline.

6.1.2. Handling of Dropouts or Missing Data

In general, no data will be imputed. Missing intermediate or final measurements of the anthropometric measurements will not be replaced by imputed values.

6.1.3. Analysis Visit Windows

As per the protocol, a window of ± 3 weeks is allowed for the follow-up visits (Visits 2 to 20), while the Screening visit is planned within 1 month before the Baseline visit.

Statistical analyses will be based on scheduled visits collected in the eCRF without further realignment.

6.1.4. Pooling of Sites

Sites will not be taken into account in the analyses. Therefore, the question of pooling of sites is not applicable.

6.1.5. Derived Variables

The following derived and computed variables have been initially identified as important for the descriptive summaries:

1. Height Growth (HG) Height Standard Deviation Score (SDS) with reference to normal population
2. Height SDS with reference to achondroplasia population
3. Sitting height/standing height (%)
4. Arm span/standing height (%)
5. Difference between arm span (cm) and standing height (cm)
6. Change from baseline = (value at current timepoint – value at baseline)
7. Average of valid anthropometric measurements. When it is required to perform 3 valid measurements, the average of the 3 will be used in descriptive summaries. If 1 or 2

valid measurement are missing, the average will include only non-missing values. If all 3 measurements are missing then the average will be missing as well.

8. Age at baseline

Age at baseline = (date of informed consent – date of birth)/365.25

Age will be rounded using 2 decimal places. If the day of birth is missing, but the month and year are present, age will be calculated based on day 1 if the month and year match the month/year of informed consent, or 15 if not. If the month is missing, age will be set to missing.

9. Exact age at each visit

- Exact age in years = (date of visit – date of birth)/365.25
- Exact age in month = (date of visit – date of birth)/30.4375
- Exact age in days = (date of visit – date of birth)

The exact age (2 decimal places if in months, 3 decimal places if in years) will be used to calculate the height-for-age SDS. The use of the 2 date variables (date of birth and date of visit) for calculating the exact age of the child is the recommended approach as best practice. If the day is missing for the date of birth, 15 will replace it, unless the month and year of birth match the month and year of informed consent in which case the first of the month will be used. If the month is missing for the date of birth, the exact age values and the height-for age SDS will be set to missing.

10. Age groups at each visit. Three age groups will be identified: <2 years, 2-10 years, and ≥10 years. Children may move from an age group to the next one during the study.

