8. RESEARCH METHODS

8.1. Study Design

This is a prospective, registry study, to be conducted at multiple clinical centers globally, in which participants with achondroplasia will be followed over a five-year period with respect to achondroplasia symptoms, tests & treatments, anthropometric parameters and biomarkers of bone growth collagen X, CNP/proCNP, CTX and P1NP. No study drug will be administered, and no other type of therapy will be provided.

There will be a Screening visit, a Baseline visit, 3-month interval visits (± 3 weeks) including an annual visit every 12 months and an end of study visit. The end of study visit will be scheduled (or a given visit will be considered the end of study visit) as soon as any of the following criteria is met:

- Growth plates are considered to have fused, defined as standing height gain less than 1 cm within the last 6 months;
- The participant has reached end of puberty (Tanner Stage V);
- The participant is enrolled in any interventional study;
- The participant is diagnosed or develops any of the conditions related to exclusion criteria 1, 2 & 6;
- The participant is to receive any growth hormone, insulin-like growth factor 1 (IGF-1), anabolic steroids, or any other drug expected to affect growth velocity;
- The participant has participated in the study for 5 years;

- The participant is considered lost to follow-up.

The end of this study is defined as the date of the last visit of the last child participating in the study.

The study will enroll participants in the following approximate proportions:

- 40% 0-5y;
- 40% 5-10y;
- 20% 10-15y.

Any treatment received during the study in relation to important medical events and any treatment based on the medical judgment of the investigator that may affect the participant's growth trajectory must be recorded in the eCRF:

- Description of the treatment (for medical treatment: route of administration, frequency and dose);
- Indication;
- Start and stop date.

Treatment is defined as any medical, surgical or other intervention to treat the underlying condition.

The rationale for the study design is summarised as follows:

A prospective longitudinal design is selected to collect blood samples and anthropometric data simultaneously in a standardized fashion, and thereby allowing for estimation of between and within participant variability laboratory parameters as well as testing for possible correlations between laboratory parameters and growth.

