2.2.3.2. Derived Anthropometric Endpoints

Five additional anthropometric endpoints will be derived:

1. Height Growth (HG)

$$HG_i = \frac{OH_i - OH_0}{RH_i - RH_0}$$

where:

OH_i = Observed Height in cm at visit i

OH_0 = Observed Height in cm at baseline

RH_i = Achondroplasia Reference Height at i (Merker et al., 2018)⁹

RH_0 = Achondroplasia Reference Height at baseline

HG will be calculated every 3 months after baseline.

2. Sitting height/standing height (%)

The ratio (%) between the sitting height and the standing height will be calculated for all subjects.

3. Arm span/standing height (%)

The ratio (%) between the arm span and the standing height will be calculated for all subjects.

4. Difference between arm span and standing height (cm)

The difference between the arm span and the standing height will be calculated as:
arm span (cm) – standing height (cm)

5. Height Standard Deviation Score (SDS)

The SDS for a given height or length in cm will be calculated using the LMS method

$$SDS = \frac{\left(\frac{\text{height in cm}}{M}\right)^L - 1}{LS}, \quad L \neq 0$$

$$SDS = \frac{1}{S} \ln\left(\frac{\text{height in cm}}{M}\right), \quad L = 0$$

where L, M, and S are the interpolated values between the neighbouring values from the standard tables corresponding to the gender and to the exact age of the child. If the month is missing in the date of birth then the SDS will be set to missing.

L, M, and S, provided in the standard tables, are the tabulated fitted values of Box-Cox power, median, and coefficient of variation corresponding to the standard population, respectively.

If $L=1$ the formula for calculating the SDS can be written as:

$$SDS = \frac{\text{observed value} - \text{median value of the reference population}}{\text{standard deviation value of the reference population}}$$

where the median value is M and the standard deviation is $M \times S$.

The same method will be applied for both the standing height and the recumbent length.

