7.3. Demographics and Other Baseline Characteristics

Summary statistics for exact age at the Baseline visit, gender, race, ethnicity, and achondroplasia familiarity will be presented by gender.

For the continuous variables, the number of non-missing values and the mean, SD, minimum, median, and maximum will be tabulated.

The number and percent of subjects reporting various medical and surgical histories, grouped by Medical Dictionary for Regulatory Activities (MedDRA) system organ class (SOC) and preferred term (PT) (coded using MedDRA v.20.0), will be tabulated by gender. Medical and surgical histories by SOC and PT will be sorted in order of descending frequency in the overall group of the SOC and then by descending frequency orders of the PT within each SOC.

8. Analysis of the Anthropometric Endpoints

Descriptive summaries of the observed value and change from baseline will be calculated for the anthropometric endpoints. For continuous variables, number of non-missing values, number of

missing values, the mean, SD, minimum, median, and maximum will be tabulated by gender. Subgroup analysis will be performed by age group at each visit.

Angles are circular quantities and are usually described using polar coordinates since the arithmetic mean may not be appropriate. However, angles for elbow and knee extension measure the deviation from a completely straight elbow or knee and are not circular quantities. The elbow extension angle and the knee extension angle will be summarized using the same descriptive statistics described for other anthropometric endpoints.

Height growth, height SDS, ration between sitting and standing heights, and ratio between arm span and standing height will be plotted against age separately by gender.

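### Change from baseline is tabulated by age group at the visit, so the 2–10 and ≥10 rows carry growth from a younger age group

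*SAP*

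**What the plan says.** Four provisions of the SAP act together.

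- **Grouping (6.1.5, item 10).** "Age groups at each visit. Three age groups will be identified: <2 years, 2-10 years, and ≥10 years". It adds: "Children may move from an age group to the next one during the study".
- **Baseline (6.1.1).** "The observation recorded at Baseline visit (Visit 1) will be used as the baseline observation for all calculations of change from baseline". Item 6 of 6.1.5 defines change as the current value minus the baseline value.
- **Summaries (section 8).** "Descriptive summaries of the observed value and change from baseline will be calculated for the anthropometric endpoints", and then "Subgroup analysis will be performed by age group at each visit".
- **Height Growth (2.2.3.2).** This is the observed gain since baseline divided by the reference gain since baseline. "HG will be calculated every 3 months after baseline".

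Table 4 of the SAP attaches the label 'Age groups' to 15 by-visit tables: knee height, head circumference, arm span, two joint angles, body weight, three cranial measures, waist, chest, Height Growth, two ratios, and the arm span–height difference. Knee height, head circumference and arm span are primary endpoints in Protocol section 7. The two standing-height and supine-length tables and the two height SDS tables do not carry the label.

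Protocol 11.5 asks for subgroups by age group without saying whether age is taken at baseline or at the visit.

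**The concern.** Change from baseline accumulates from entry, while the age label is refreshed at every visit. A child who passes age 2 or age 10 takes all growth since entry into the older group's row. No rule resets the baseline at the crossing, groups change by entry age, or restricts growth to time spent inside one group.

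Protocol 11.5 gives the main purpose as reference data for future interventional studies. Someone planning a trial in children of 10 or older could read the Month 60 change in arm span under ≥10 as growth at that age, when much of it was gained before 10. The membership of each group also changes from visit to visit, so reading down a group's rows does not show how any fixed set of children grew.

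**Working it through.** The plan gives no figure for this point, so there is none to reproduce.

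**Inputs.** About 300 children (Protocol Summary) and up to 5 years of follow-up. Enrolment is 40% aged 0–5, 40% aged 5–10 and 20% aged 10–15 (Protocol 8.1: "The study will enroll participants in the following approximate proportions"; repeated in SAP 3.1).

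**Assumptions (not in the documents).** Ages are uniform within each band and nobody leaves. This gives 120/5 = 24 children per year of age from 0 to 10, and 60/5 = 12 from 10 to 15.

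**Step 1: which rows can hold growth from another group.** Baseline age = visit age − time since baseline. Age only rises, so a child under 2 at a visit was under 2 at baseline. The share of <2 rows from another group is 0%, with no assumption. Rows for 2–10 and ≥10 can hold growth from below their lower limit.

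**Step 2: share of each row that was in a younger group at baseline.**

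| Visit | <2: n | 2–10: from <2 / row | ≥10: from 2–10 / row |
|---|---|---|---|
| Baseline | 48 | 0 / 192 | 0 / 60 |
| Month 12 | 24 | 24 / 192 = 12.5% | 24 / 84 = 29% |
| Month 24 | 0 | 48 / 192 = 25% | 48 / 108 = 44% |
| Month 60 | 0 | 48 / 120 = 40% | 120 / 180 = 67% |

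For example, the Month 60 row for ≥10 holds everyone who entered at 5 or older: 120 + 60 = 180, of whom 120 entered below 10.

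**Step 3: sensitivity.**

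- *2–10 row.* This depends on ages within the 0–5 band. If density falls linearly with age, the share under 2 at entry is 1 − (3/5)² = 64%. If it rises linearly, the share is (2/5)² = 16%. The row shares become 7–19% at Month 12, 10–40% at Month 24 and 16–64% at Month 60.
- *≥10 row at Month 60.* Without exits this does not depend on ages within bands, because every 5–10 entrant has reached 10: 40/(40 + 20) = 67%. If half of the 10–15 entrants leave, it is 120/150 = 80%. If instead half of the 5–10 entrants leave, it is 60/120 = 50%.

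**Step 4: child-years outside the labelled age, out of 300 × 5 = 1,500 at Month 60.**

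- *Age at visit (current rule).* Time before 2 in the 2–10 row: 24 × ∫₀²(2 − a)da = 24 × 2 = 48, which is 8% of that row's 600. Time before 10 in the ≥10 row: 24 × ∫₅¹⁰(10 − a)da = 24 × 12.5 = 300, which is 33% of that row's 900. Total 348 (23%).
- *Age at baseline.* Time after 2 among entrants under 2: 48 × 5 − 48 = 192. Time after 10 among entrants at 5–10: 120 × 5 − 300 = 300. Total 492 (33%).
- *12-month gains classified by midpoint age.* Each of the 48 + 120 = 168 boundary crossings falls inside one interval. The part on the wrong side averages a quarter of a year: 168 × 0.25 = 42 (3%).

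**The case against.** The strongest reply is that the choice between age at visit and age at baseline is one of estimand, and that grouping by baseline age fits the label less well: 492 child-years outside it, against 348. That stands. Baseline-age rows describe a fixed cohort, not growth at a stated age, so regrouping alone would not be enough.

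A second reply is that growth by age appears elsewhere. Height Growth, SDS and two ratios are plotted against age. SDS and the arm span–height difference are modelled on continuous age. Individual data are listed, and no hypothesis is tested. This lowers the severity. But knee height, head circumference and arm span itself have no planned plot or model against age, so the by-visit tables are the only planned summary of their growth.

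Three stronger readings are tempting, and the documents do not support them.

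- *All three groups are contaminated.* Step 1 rules this out for <2. Those rows are depleted, which is a different problem.
- *The distortion can be stated in centimetres of height.* Table 4 does not label the height tables by age group, although the general sentence in section 8 is broader and the table shells are not available. The SAP does not say that change is computed from supine length to standing height. SAP Appendix 2 prints achondroplasia medians only at 1.5 to 3 years and at 7 and 8 years, so a height effect in the ≥10 row would rest on an assumed curve.
- *Height Growth is distorted as much as raw change.* It divides by the reference gain over the same interval, so a child who tracks the reference scores 1 at any age. Only departures from the reference that arose earlier are placed under the later label.

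**Conclusion.** The point holds for change from baseline in the 2–10 and ≥10 rows of the tables split by age group, and to a lesser degree for Height Growth. At Month 60 about 40% of the 2–10 row (16–64% over the age skews tried) and 67% of the ≥10 row (50–80% over the exit patterns tried) were in a younger group at baseline. These are shares of children, not sizes of bias; on the same assumptions the share of follow-up time spent in the younger group is 8% and 33%. The direction and the 0% for <2 follow from the SAP text alone. The other percentages rest on the planned mix and on the stated assumptions about age and exits. Observed values by current age need no change. This should be fixed before the tables are produced; it does not undermine the data collected.

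**What to change.** Amend SAP 6.1.5 item 10, section 8 and the affected shells as follows.

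1. Keep age at the visit as the grouping for observed values.
2. Group change from baseline and Height Growth by age at baseline, and label the rows as baseline-age cohorts so that they are not read as growth at the stated age.
3. Require, rather than merely allow, a table of gains between visits (for example over 12 months) classified by age at the interval midpoint. This is the table that describes growth at a given age. For height it would also come close to the annual growth velocity that Protocol 11.5 lists and SAP 2.2.3.2 does not derive.
4. State whether a change is computed when a child moves from supine to standing measurement, or is set to missing.

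The cost is SAP wording, one grouping variable and one extra table layout. Age at baseline and exact age at each visit are already derived (6.1.5, items 8 and 9), so no new data are needed.
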